### Blood transcriptomics

For blood transcriptomics at least the following analyses will be conducted. The PP population will be primarily used.

Unsupervised clustering of the samples will be conducted. Clustering will be done at DuPont and in case clusters are formed, the clustering information (per sample per subject) will be provided to 4Pharma for further the analyses described below.

- Timepoint and treatment effect on clustering will be investigated with categorical repeated measures models, where clustering is the outcome variable, and timepoint, treatment, interaction of treatment and timepoint are included as fixed effects.
- Effect of cohort, infection (yes/ no) and illness (yes/ no) on clustering will be investigated with the above described model by including separately each factor to the analysis model.
- The effect of D-28/D0 clustering on the following outcome variables will be investigated by adding the cluster as a fixed effect to the analysis models: Duration of illness, viral shedding, clinical symptom severity score and immune markers. For symptom scores, the analysis models have already been described in 11.2.5 and 11.2.6. Also, for immune markers the analysis model to be used has already been described in this chapter. For duration of illness an analysis of covariance (ANCOVA) model will be used including treatment and cluster effect in the model. The analysis will be conducted using the Ill population. For viral shedding a logistic regression model with treatment and cluster effect will be fitted and infected population used. For all models, also fixed interaction effect of treatment and cluster may be investigated.

In addition to the clustering, correlations between individual genes from throat and nasal metagenomics will be calculated, if feasible. For the correlations FDR correction will be used with the p-values.

Connections between the exploratory data/ results and efficacy and other endpoints may be investigated with suitable analysis models (will be described in the Documentation of the Statistical Methods, if done). Part of the exploratory analyses (microbiota and transcriptomics) will not be included in the Statistical Study Report.

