2.2.3 Exploratory objectives

- To study the effect of the probiotic on blood transcriptome during basal state and infection.
- To validate the effect of the probiotic on nasal cytokine profile at baseline and during infection
- To characterize the nasal, throat, and intestinal microbiomes before and during rhinovirus infection and supplementation period.
- To investigate correlations between specific microbiome profiles, immune responses and subsequent infection and illness.
- To compare with a cold questionnaire

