4.2.2 Study periods

Screening:

- Consent and enrollment (approximately 375 subjects)
- Medical history questionnaire and demographics
- Vital signs and brief physical exam
- Physical activity question
- Review of inclusion/exclusion criteria
- Blood draw for screening neutralization antibody titer (if no antibody screening test has been done in the last 12 weeks)

Day -42 ± 4:

- All subjects begin dietary “run-in” period

Day -28 ± 4: Seronegative subjects only

- Review of inclusion/exclusion criteria
- Pre-probiotic baseline nasal lavage for IL-8 and other cytokines
- Pre-probiotic baseline nasal swab for microbiomics
- Pre-probiotic baseline throat swab for microbiomics
- Blood draw for pre-probiotic transcriptomics studies
- Assessment of concomitant medications
- Randomized to active or placebo probiotic
- Urine pregnancy screen for females

Day -21 ± 2

- All subjects return to study site for new supply of probiotic and compliance review
- AE assessment
- Assessment of concomitant medications

Day -14 ± 2:

- All subjects return to study site for new supply of probiotic and compliance review
- Nasal lavage for multiplex cytokine assays
- AE assessment
- Assessment of concomitant medications

Day -7 ± 2:

- All subjects return to study site for new supply of probiotic and compliance review
- AE assessment
- Assessment of concomitant medications

Day 0:

- Review of inclusion/exclusion criteria
- Assessment of blinding
- AE assessment
- Assessment of concomitant medications
- Urine pregnancy screen for females
- Stool specimen for probiotic compliance and microbiomics
- Nasal swab for microbiomics
- Throat swab for microbiomics
- Throat swab for culture
- Nasal lavage for unanticipated viruses
- Nasal lavage for pre-RV challenge baseline IL-8
- Blood draw for measurement of neutralizing antibody
- Blood draw for pre-RV challenge transcriptomics
- Nasal lavage for multiplex cytokine assays
- Symptom assessment
- Challenge with rhinovirus
- Compliance check/resupply
- Continue probiotic treatment

Day 1-4:

- AE assessment
- Assessment of concomitant medications
- Nasal lavage for quantitative rhinovirus culture
- Nasal lavage for IL-8 measurement
- Nasal lavage for multiplex cytokine assays
- Symptom assessment
- Assessment of the effect of symptoms on physical activity
- Nasal swab for microbiomics (day 3)
- Throat swab for microbiomics (day 3)
- Blood draw for post-RV challenge transcriptomics (Day 2 only)
- Continue probiotic treatment

Day 5:

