6.4 Exploratory endpoints

6.4.1 Cytokine response of nasal mucosa

6.4.1.1 Interleukin-8 assay: Concentrations of interleukin-8 in nasal lavage are determined with a commercially available ELISA assay (R&D Systems, Minneapolis, MN). The lower limit of detection for the assay is 31.25 pg/mL. The precision of the assay for measurement of IL-8 in nasal wash has been determined with pools of nasal wash spiked with known concentrations of IL-8. Intra-assay variability was found to range from 3.8-5.7% and inter-assay variability was found to range from 2.7-11% for nasal wash containing high and low concentrations of IL-8, respectively. The recovery of IL-8 in nasal wash ranged from 88-136% of predicted. Specimens that have IL-8 concentrations greater than the operating range of the assay will be diluted 1:10 and 1:100 and re-assayed.

6.4.2 *Multiplex assays: A panel of cytokines and chemokines (TGF- β 1, GCSF, GMCSF, IFN- γ , IL-1 α , IL-12p70, IL-15, CCL20, IL-1 β , IL-6, IL-10, CXCL10, CCL2, CCL3, CCL5, TNF- α) may be measured in nasal lavage fluid using a commercially available multiplex assay (Aushon BioSystems, Inc., Billerica, MA). A determination of which assays will be included will be made as a post-hoc exploratory analysis. Blood transcriptomics*

6.4.2.1 Collection of specimens: The effect of probiotics on gene expression before and after rhinovirus challenge will be determined by comparing expression in the probiotic and placebo groups on study days -28, 0 and 2. Expression analysis will be done on peripheral blood specimens by microarrays targeted at inflammatory and antiviral genes. Blood samples will be collected in PAXgene RNA tubes (PreAnalytix) and stored at -80°C until shipping. Samples will be shipped on dry ice to DuPont Haskell Global Centers for Health and Environmental Science and immediately stored at -80°C until further processing. RNA will be isolated from blood stored in PAXgene tubes using a PAXgene Blood RNA isolation kit (Qiagen) and potential DNA contamination will be removed with on-column DNase treatment. RNA concentration and quality will be verified on a Nanodrop® spectrophotometer (NanoDrop) or with a Quant-iT™ RiboGreen® RNA Assay Kit (Thermo Fisher). RNA integrity will be determined with an Agilent Bioanalyzer 2100 (Agilent). All RNA samples processed for RNA-sequencing should have a 260/280 absorption ratio greater than 2 and a RNA integrity number (RIN) greater than 9.8.

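### The blood-transcriptome cluster model fits one infection (or illness) coefficient over two pre-challenge samples and one post-challenge sample, so it dilutes a Day 2 change and cannot separate it from a prior difference

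*SAP*

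**What the plan says.** The first bullet of SAP 11.3, Blood transcriptomics, sets up a categorical repeated measures model in which "clustering is the outcome variable, and timepoint, treatment, interaction of treatment and timepoint are included as fixed effects". The second bullet reuses it: "Effect of cohort, infection (yes/ no) and illness (yes/ no) on clustering will be investigated with the above described model by including separately each factor". No interaction of infection or illness with timepoint is named, nor any restriction to Day 2 or adjustment for an earlier sample. The third bullet turns the question round: "The effect of D-28/D0 clustering on the following outcome variables will be investigated by adding the cluster as a fixed effect". Its outcomes are illness duration, viral shedding, symptom severity and immune markers.

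Protocol 6.4.2.1 gives the sampling scheme: "comparing expression in the probiotic and placebo groups on study days -28, 0 and 2". Protocol 4.2.2 places these draws relative to the virus. The Day 0 list has "Blood draw for pre-RV challenge transcriptomics", and the Day 1-4 list has "Blood draw for post-RV challenge transcriptomics (Day 2 only". Infection and illness are defined from events after challenge (SAP 11.1), and each takes one value per subject.

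**The concern.** The second bullet asks how infection and illness affect the cluster into which a blood sample falls. Only one of the three samples can show such an effect. Because the factor enters as a single term, the null being tested is that later infection (or illness) has no association with cluster over all three days together. The treatment-by-timepoint term does not help: it lets the arm difference vary by day, not the infection or illness difference.

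Two things follow. A change that exists only on Day 2 is watered down by two samples in which it cannot occur. And if people who later become infected or ill already differed before challenge, the test can reject although the virus changed nothing. At stake is the interpretation of one exploratory result.

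**Working it through.** **The reading of the model.** The SAP writes out the parallel model for microbiota clusters (end of the microbiota part of 11.3). There cohort is a plain main effect and treatment-by-timepoint is the only interaction. Where the SAP wants an interaction it names one (subgroup by treatment in 11.4, treatment by cluster in the third transcriptomics bullet). Where it wants the virus effect isolated it also says so: the strain qPCR analysis has an extra model restricted to observations after Day 0. Transcriptomics has no counterpart. The main-effect reading is therefore the natural one.

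**Algebra (two clusters, for illustration).** Let F be infection or illness. The planned model is logit P(cluster) = timepoint + treatment + treatment×timepoint + δ·F. Suppose the true log odds ratio for F is π on Day -28 and Day 0, and π + θ on Day 2. Here π is the prior difference and θ the post-challenge change. With roughly equal weight per day:

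- planned coefficient: δ ≈ [π + π + (π + θ)]/3 = π + θ/3;
- Day 2 minus the mean of the two earlier days: (π + θ) − (π + π)/2 = θ.

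One number, δ, carries two unknowns. The equal weighting is approximate, because a logit model weights days by information.

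**The plan's own figure.** The documents give no power or effect size for this analysis. The only sample-size figure is 95 completed subjects per arm for 60% versus 40% illness (Protocol 8.1). With pooled variance, n = [1.96·√0.50 + 0.842·√0.48]²/0.20² = 96.9, or 97 per arm. With unpooled variance, (1.96 + 0.842)²·0.48/0.04 = 94.2, or 95. The figure is reproduced, and 2 × 95 = 190 is used below as the per-protocol size.

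**Simulation inputs.** From the documents: 190 subjects, 1:1 allocation, three sampling days, illness 60%/40% by arm, infection 90%, two-sided 5%. Assumed, because the documents are silent: two clusters, pre-challenge cluster prevalence 30%, subject random-effect SD 1 on the logit scale, within-subject odds ratios 2 to 10. Tests are logistic GEE with robust standard errors, 1,000 runs per cell, so the Monte Carlo standard error is at most √(0.25/1000) = 1.6 points.

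Rejection rates at nominal 5%:

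| Scenario | Test | OR 2 | OR 3 | OR 5 | OR 10 |
|---|---|---|---|---|---|
| Illness, Day 2 change only | planned | 15% | 33% | 62% | 90% |
| | contrast | 34% | 73% | 97% | 100% |
| Infection, Day 2 change only | planned | 9% | 15% | 26% | 45% |
| | contrast | 17% | 32% | 58% | 86% |
| Illness, prior difference only | planned | 80% | 99% | 100% | 100% |
| Infection, prior difference only | planned | 37% | 74% | 97% | 100% |
| Either, prior difference only | contrast | about 4-7% throughout | | | |

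**Check against the algebra.** For illness at OR 3, the contrast estimates a log odds ratio of 0.92 and the planned coefficient 0.32; 0.92/3 = 0.31.

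**Smaller prior differences.** A separate simulation used linear models with robust variance, 50% ill or 88% infected, and 4,000 runs. A prior difference of about 9 points in cluster share made the planned test reject 51% (illness) and 30% (infection) of the time, against 5% and 6% for the contrast. At 4-5 points the planned test rejected 17% and 14%.

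**Sensitivity to cluster prevalence.** The comparator here is a Day 2-only model for illness. With 5% pre-challenge prevalence, power is 58% against 83% (Day 2 shares 20% versus 40%) and 88% against 98% (30% versus 60%). With 30% prevalence the same Day 2 differences give 31% against 83% and 53% against 98%.

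**The case against.** The strongest defence is that little hangs on this. The analysis is exploratory, runs only if clusters form, and is introduced as a minimum list, so an interaction is permitted. The same sentence speaks of an effect of cohort, which is ordinary model-term language, and the SAP nowhere says that the coefficient will be reported as virus-induced. All of this stands. It limits the weight of the point but does not supply the missing term.

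A reader might infer three stronger things that the documents do not support.

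- *That the planned test misses a true Day 2 effect.* It dilutes one and often fails to detect it. A large illness effect is still found 90% of the time at OR 10 with SD 1 (55% with SD 2, 98% with SD 0.5). A cluster that is rare before challenge loses much less power. The near three-fold dilution belongs to the 30% prevalence scenario and is not general.
- *That a protocol objective is compromised.* Protocol 2.2.3 reads "To study the effect of the probiotic on blood transcriptome during basal state and infection". That is a treatment question, answered by the treatment-by-timepoint term in the first bullet, which is unaffected.
- *That the third bullet already covers the prior association.* It does not. Infection yes/no and illness yes/no are not among its outcomes; duration is analysed only in the Ill set and shedding only in infected subjects.

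**Conclusion.** The point holds as a minor one. As written, the second bullet cannot separate a post-challenge change from a pre-existing difference, and it has less power for a Day 2 change in every scenario tried. That the coefficient mixes the two follows from the sampling days and the stated model terms alone. The size rests on assumptions about the number of clusters, their prevalence and the subject variance, none of which the documents give. Cohort is not affected, because it is fixed before any sample is taken. Talk of cause and effect being reversed would go too far: that depends on how the result is worded in the report, which the SAP does not fix. No primary, secondary or safety conclusion depends on this analysis.

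**What to change.** In the second bullet of SAP 11.3, Blood transcriptomics, add the factor-by-timepoint interaction for infection and for illness. Take the Day 2 contrast relative to the pre-challenge contrast (Day -28 and Day 0) as the post-challenge association. Report the pre-challenge contrast from the same model separately, as a prior association. Leave cohort as a main effect.

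The cost is a sentence or two of SAP wording, one extra model term for each of the two factors, a few degrees of freedom and no new data. Three limits should be stated with it:

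- The change contrast has slightly less power than a plain Day 2 comparison (72% against 80% in the separate simulation, for illness with a 20-point Day 2 difference).
- The infection contrast stays weak. With about 90% infected, only about 190 × 0.10 = 19 subjects are uninfected, and power is 32% at OR 3 and 58% at OR 5.
- Illness is scored over Days 1-5, so the Day 2 blood precedes part of the outcome. The illness contrast is an association, not a clean causal effect.

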## **11.4 Sensitivity analyses**

As a sensitivity analysis, a logistic regression will be computed for the primary efficacy variable. In addition to the treatment effect also potential confounding factors, such as antibody status, cohort, gender or incidence of wild-type virus, are one by one included to the model as fixed effects. Also, the interaction effect (subgroup\*treatment) will be investigated.

## 12 Cold questionnaire comparison

Alternative cold questionnaire from earlier study conducted by West et al. (AUSTRALIA) study will be used to define the illness episodes. Illness episodes defined based on the modified Jackson criteria will be compared with the AUSTRALIA defined episodes and investigated if both questionnaires identify the same episodes. Number of episodes identified by both questionnaires and only one questionnaire will be summarized descriptively. Since training was part of the AUSTRALIA criteria, if the subject had been training was asked also in this study in addition to the modified Jackson criteria. Thus AUSTRALIA defined episodes will be compared both to modified Jackson with training and to modified Jackson regardless of training defined episodes.

## 13 Analysis of safety and tolerability

All subjects who have been randomised to the study and used the study products will be included in the safety analysis.

### 13.1 Adverse events

Adverse events will be tabulated by treatment group, system organ class, preferred term, causality and severity. Both subject and event counts will be calculated. In addition, SAEs and AEs leading to discontinuation will be summarized. Adverse events reported for more than 5 % of the patients in either treatment group will be tested using the Fisher's exact test.

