
• Secondary efficacy• Exploratory endpoints	
Secondary efficacy
 
• Duration of illness episodes• Infection rate• Viral load• Proportion shedding the virus 
Exploratory endpoints
 
• Blood transcriptomics• Fecal, nasal, and throat microbiota• Nasal cytokine response• Cold questionnaire comparison

Safety
	
AEs and SAEs will be followed throughout the trial

Statistics
	
Sample size A sample size of 95 completed subjects/arm would be expected to detect a reduction in rhinovirus-induced illness of 20% (from 60% to 40%) with 80% power with $p_{\alpha} = 0.05$.
 
Methodology The primary endpoint, the incidence of rhinovirus-associated illness episodes between the treatment groups will be tested with a chi-square test and logistic regression model.
 
T-test, Mann-Whitney U test, chi-square test and ANOVA will be used for secondary parameters.
 
Descriptive statistics for safety and other variables will be reported.

ABBREVIATIONS

ADR	Adverse Drug Reaction
AE	Adverse Event
BI-04	Bifidobacterium animalis subsp. lactis BI-04
eCRF	Electronic Case Report Form
CSR	Clinical Study Report
DMP	Data Management Plan
DVP	Data Validation Plan
EIA	Enzyme Immunoassay
ELISA	Enzyme Linked Immunosorbent Assay
GCP	Good Clinical Practice
HLA	Human Leukocyte Antigen
IB	Investigator's Brochure
ICH	International Conference on Harmonisation
IEC	Independent Ethical Committee
IP	Investigational Product
IRB	Institutional Review Board
ITT	Intended To Treat
MedDRA	Medical Dictionary for Regulatory Activities
NSAID	Nonsteroidal anti-inflammatory drugs
PBMC	Peripheral Blood Mononuclear Cells
qPCR	Quantitative Polymerase Chain Reaction
RV	Rhinovirus
SAE	Serious Adverse Event
TMF	Trial Master File

SCHEDULE OF EVENTS

	Screening	Day -28	Day -21	Day -14	Day -7	Day 0	Day 1	Day 2	Day 3	Day 4	Day 5	Day 6-14	Day 21-28
Consent	x												
Review of inclusion/exclusion	x					x							
Serum neutralizing antibody	x*					x							x
Urine Pregnancy Screen for females		x				x							
Start of dietary run-in period	x												
Compliance check/resupply			x	x	x	x							
Probiotic/placebo treatment		x	x	x	x	x	x	x	x	x	x	x	
Assessment of blinding						x							
Nasal swab for microbiomics		x				x			x				
Throat swab for microbiomics		x				x			x		x	x(14)	
Throat swab for culture						x					x		
Fecal sample for microbiomics						x							

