Reference	Number and characteristics of subjects consuming BI-04	Supplementation dose and length	Adverse events
[name] et al. 2015; Unpublished	95/190 Adults (Mean 22 yrs)	2×10^9 CFU/d for 32 d	Gastrointestinal AEs occurred only in the active group ($P < 0.01$). AEs in 5 subjects (4 GI, 1 Respiratory illness) were judged, prior to unblinding, to be possibly or probably related to the study interventions.
[5, 6, 14]	161/465 Adults (average 36 y) Physically active	2×10^9 CFU/d for 150 d	2 subjects withdrew because of uncomfortable GI symptoms
[15]	336/503 Adults (30-70 y) Receiving antibiotics	4.3×10^9 CFU/d (n=168) or 1×10^9 CFU/d (n=168) in a mixture of four strains for 10 to 21 d	AE rates were 7.2%, 4.2% and 4.2% in the placebo, high-dose and low-dose groups, respectively (AEs were allergy to sea food, arrhythmia, fever, headache, left upper arm fracture, runny nose and vomiting) One SAE was reported (death due to myocardial infarction; the subject had a history of coronary heart disease) None of the AEs were considered to be related to the study product High-dose probiotic group had fewer drop-outs than low-dose or placebo group
[16]	24 / 47 Children (mean 9 yrs) with history of allergy	1.25×10^9 CFU/d with one other strain for 122 d	2 subjects dropped out in probiotic group, no reason published
[17]	20/40 Adults (18-45y) Consuming antibiotics	1×10^{10} CFU/d in a mixture of five strains for 20 d	No significant difference in AE rate between treatment groups (both groups consumed antibiotics) Most common AEs were diarrhea (3 in active and 1 in placebo group), vaginal yeast infection (4 in active and 1 in placebo group) and abdominal pain (3 in probiotic and 3 in active group)
[18]	9/86 Adults (18-64 y) Oral cholera vaccine given	2×10^{10} CFU/d for 3 w	None documented
[19]	20/40 Adults (>18y) Consuming antibiotics	5×10^9 CFU/d in a mixture of five strains for 20 d	None documented
[7]	9/18 Healthy elderly	3.5×10^{10} CFU/d in a mixture with inulin and Bb-02 for 28 days	None documented

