6.4.4.1 Bacterial DNA will be isolated from the swabs and feces by using MagMAX™ Total Nucleic Acid Isolation Kit (Applied Biosystems, Bridgewater, NJ). Human DNA may be quantified for analysing the ratio of human and bacterial DNA by using housekeeping genes that do not allow subject identification. The composition of microbiota will be analyzed by next-generation sequencing (or equivalent) technology for identification of microbial species in the samples. The data will be analyzed to determine effects of probiotic on both abundance and diversity of bacterial species. . In addition, single strain targeting PCR-based molecular methods (i.e. qPCR, digital PCR or equivalent) will be applied to detect the supplemented probiotic strain, BI-04.

6.4.4.2 Throat swabs will be collected on study days 0, 5, and 14 for detection of pharyngeal pathogens by culture and qPCR. A single swab will be sent to the microbiology laboratory at the University of Virginia for detection of *S. aureus*, pneumococcus, *H. influenza*, meningococcus and group A streptococcus.

6.4.5 *Cold questionnaire comparison*

Performance of the questionnaire used in the West study [5] will be compared to endpoints of this study.

6.5 **Assessment of safety**

6.5.1 *Adverse events*

6.5.1.1 The safety of the study interventions will be assessed by monitoring of adverse events. Volunteers will be asked at each study visit to report any unexpected events whether or not they are apparently study related. Each event will be recorded and an assessment of relatedness to the study interventions will be made by the investigator. Adverse events will be coded according to established standards (MedDRA). The analysis will compare both total and related events in the probiotic and the control group.

7 **Adverse Events**

7.1 **Adverse event**

7.1.1 *Definitions*

7.1.1.1 An adverse event (AE) is any untoward, undesired, or unplanned event in the form of signs, symptoms, disease, or laboratory or physiologic observations occurring in a

person given an IP in a clinical study. The event does not need to be causally related to the IP or the clinical study. An AE includes, but is not limited to the following:

- Any clinically significant worsening of a pre-existing condition.
- An AE occurring from overdose of an IP, whether accidental or intentional. Overdose is a dose greater than specified in the protocol.
- An AE occurring from abuse (e.g., use for non-clinical reasons) of an IP.

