7.1.2 Assessment of Adverse Events

For the purposes of this study using experimental rhinovirus infection, physical signs and symptoms that are expected to be associated with the common cold should not be reported as adverse events. The following physical signs and symptoms are expected to be associated with the common cold: nasal obstruction (nasal stuffiness), coryza (runny nose), sore throat, cough, sneezing, myalgia, headache, feverishness, chills, loss of appetite and malaise.

Information regarding common cold-related complications must be documented appropriately. Common cold-related complications include bronchitis, bronchospasm or exacerbation of asthma, sinusitis and otitis media. For common cold-related complications, the following information should be documented: onset date, severity, seriousness, relationship to study therapy, action taken regarding study therapy, outcome, and therapy given for event.

Some subjects may experience gut discomfort during the study product consumption. The symptoms that have been associated with use of bifidobacteria include bloating, flatulence and abdominal pain. The subjects should contact the study staff in the case that symptoms persist.

Assessment of all adverse events will include recording the time of onset and resolution of the event, severity, intervention, and an attribution by the investigator of whether the event was related to the study product.

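### SAP 13.1 tests only adverse events above 5% in an arm, leaves the coding level open, and prespecifies no test for any AE, related AEs or gastrointestinal AEs as a class

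*SAP*

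**What the plan says.** SAP 13.1 plans a table: "Adverse events will be tabulated by treatment group, system organ class, preferred term, causality and severity". It adds: "Both subject and event counts will be calculated". It then gives one test: "Adverse events reported for more than 5 % of the patients in either treatment group will be tested using the Fisher's exact test". The coding level at which the 5% is counted is not stated. No comparison is named for all AEs, related AEs or GI AEs taken together.

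Protocol 6.5.1.1 says: "The analysis will compare both total and related events in the probiotic and the control group". It names no test, and the synopsis says of safety: "Descriptive statistics for safety and other variables will be reported". SAP 2 makes safety and tolerability a secondary objective. SAP 15 lists no change to the AE analysis.

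On the known risk, Protocol Table 1 says of the earlier challenge trial (95 active of 190 subjects): "Gastrointestinal AEs occurred only in the active group", with P<0.01. Protocol 7.1.2 adds: "The symptoms that have been associated with use of bifidobacteria include bloating, flatulence and abdominal pain".

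**The concern.** GI tolerability is the product risk these documents single out. The SAP's one AE test is triggered by frequency, and the unit of counting is undefined. Bloating, flatulence and abdominal pain may be coded to different preferred terms. A GI effect of the earlier size could then exceed 5% as a class while each term stays below it. Related events, which the protocol names for comparison, are rarer and more likely to miss the cut-off.

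Whether the known risk receives a test would then depend on an unstated coding choice and on how the observed events fall across terms. The report could say that no tested AE differed between arms without the GI excess ever having been tested.

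**Working it through.** **Inputs.** Earlier trial: 95 active, 95 control, GI AEs in the active arm only, P<0.01 (Protocol Table 1; the count is not given). Related AEs in that trial: "AEs in 5 subjects (4 GI, 1 Respiratory illness) were judged, prior to unblinding, to be possibly or probably related to the study interventions". Size of this trial: 130 per arm (Protocol 4.1.1), or 254 challenged, about 127 per arm (SAP 4). Two-sided 0.05, no adjustment (SAP 7).

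**1. Count behind P<0.01.** For x/95 against 0/95 the two-sided Fisher P is 2·C(95,x)/C(190,x).

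| x | rate | Fisher, two-sided | chi-square, uncorrected | chi-square, Yates |
|---|---|---|---|---|
| 4 | 4.2% | 0.121 | 0.043 | 0.130 |
| 7 | 7.4% | 0.0139 | 0.0070 | 0.0209 |
| 8 | 8.4% | 0.0067 | 0.0039 | 0.0115 |
| 9 | 9.5% | 0.0032 | 0.0021 | 0.0063 |

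The smallest count giving P<0.01 is 7, 8 or 9, depending on the test. The 4 related GI cases cannot be the count behind it. I use 8/95 below.

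**2. The 5% rule as a count.** 0.05 × 127 = 6.35 and 0.05 × 130 = 6.5, so at least 7 subjects are needed in either case.

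**3. Rule applied by class.** P(tested) = P(X ≥ 7), X ~ Binomial(N, p), with N = 127 and 130:
- p = 7/95: 0.83 and 0.85
- p = 8/95: 0.92 and 0.93
- p = 4/95 (related GI only): 0.29 and 0.31

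**4. Rule applied by preferred term.** Take 8/95 in total, one term per affected subject, split evenly over m terms. With q = P(Binomial(N, p/m) ≥ 7), P(at least one term tested) ≈ 1 − (1 − q)^m.

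| m | p/m | q (N = 127, 130) | P(at least one tested) |
|---|---|---|---|
| 2 | 4.2% | 0.288, 0.308 | 0.49, 0.52 |
| 3 | 2.8% | 0.068, 0.075 | 0.19, 0.21 |
| 4 | 2.1% | 0.018, 0.021 | 0.07, 0.08 |

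Multinomial simulation at N = 130 gives 0.53, 0.21 and 0.08, so treating the terms as independent does little harm.

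An even split is the least favourable case. Uneven splits over three terms at N = 130 give:
- 40/30/30: 0.23
- 50/30/20: 0.35
- 60/20/20: 0.49
- 60/30/10: 0.51
- 70/20/10: 0.65

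If subjects may report several of three terms, each independently present in half of those affected, the figure is 0.54.

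**5. Power with and without the filter, as a class** (Fisher, two-sided 0.05, N = 127 to 130):

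| active rate | control rate | with 5% rule | without |
|---|---|---|---|
| 8/95 | 0% | 0.92–0.93 | 0.96–0.97 |
| 8/95 | 1% | 0.75–0.76 | 0.76–0.78 |
| 4/95 | 0% | 0.29–0.31 | 0.45–0.47 |
| 4/95 | 1% | 0.15–0.16 | 0.20 |

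**The case against.** A reader might infer that the earlier GI signal would probably go untested. The documents do not support that. A result with P<0.01 against zero implies more than 5% of the arm. If the rule runs by class, which SAP 13.1 permits because it tabulates by system organ class as well as preferred term, the signal is tested with probability 0.92 to 0.93 at 8/95, and the filter costs about four points of power. Even by term, two terms give about an even chance, and one dominant term can give 0.65.

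A reader might also infer that the SAP drops a comparison the protocol promised. That goes too far. The protocol says events will be compared, names no test, and its synopsis plans descriptive safety statistics. Tables by arm and causality, with subject and event counts, set total and related events side by side. It is therefore not shown that SAP 15 had a deviation to list. Nor does it follow that the tolerability conclusion would be wrong, because an excess such as 11 against 0 in the GI class would be visible in the required table.

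Two further points are fair. SAP 7 provides 95% confidence intervals for treatment differences in general. The table plan (SAP 20.3) is a separate file, not available here, and may contain rows for any AE and any related AE.

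All of this stands against the stronger readings. It does not supply the coding level of the 5% rule or a prespecified test for any of the three groupings, and SAP 7 does not say which AE groupings would receive an interval.

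**Conclusion.** The point holds as a gap in specification. If the GI excess recurs at 8/95, its chance of being tested is 0.92 to 0.93 by class. By term it is about 0.5 for an even split over two terms, and from 0.07 to about 0.5 over three or four, reaching 0.65 if one term takes 70% of the cases. For related GI AEs alone it is about 0.3 even by class. What is at risk is that a known signal goes untested, not that it is hidden.

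These figures assume no GI AEs in the control arm, 127 to 130 per arm in the Safety dataset and, except for the several-terms case, one term per affected subject. The count of 8 is inferred from P<0.01, and 7 to 9 are compatible with it. The documents give no distribution over terms, so the term-level figures are a range and not a forecast.

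**What to change.** In SAP 13.1, for the Safety dataset and regardless of frequency, prespecify subject-level risk differences with 95% CI and Fisher's exact test for:
- any AE
- any related AE
- any AE in the MedDRA gastrointestinal disorders class, all and related

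State that the 5% rule applies to other individual preferred terms.

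This gives the one documented product risk a fixed comparison that does not depend on observed frequency. At class level with no control events, power rises from 0.92–0.93 to 0.96–0.97 at 8/95, and from 0.29–0.31 to 0.45–0.47 for related GI AEs at 4/95. The gain is larger if the rule would otherwise run by term. The cost is SAP wording and about four table rows from data already tabulated. The downside is a few more unadjusted safety tests, in line with SAP 7, which makes no adjustment to p-values.
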